7. STUDY ASSESSMENTS AND PROCEDURES

Protocol waivers or exemptions are not allowed with the exception of immediate safety concerns. Therefore, adherence to the study design requirements, including those specified in the Time and Events Table, are essential and required for study conduct.

7.1. Time and Events Table

Protocol Activity	Pre-Screen	Screen	Treatment				Follow Up	
	Visit 0 Pre-screen	Visit 1 Screening	Visit 2 Randomisation	Visit 3	Visit 4	Visit 5	Early Withdrawal Visit	Safety Follow-up Contact
Study Week		Week -2	Week 0	Week 4	Week 12	Week 24		1 week Fw-up
Window		-3/+8d		-4/+2d	-8/+6d	-8/+6d		-1/+4d
Written Informed Consent ^a	X	X						
Genetic Informed Consent ^b	X	X						
Demography ^c	X	X						
Medical History, including cardiovascular history		X						
COPD and Exacerbation History		X						
Concomitant Medication Assessment	X	X	X	X	X	X	X	X
Inclusion/Exclusion Criteria		X						
Randomisation Criteria			X					
Smoking History		X						
Smoking status		X				X	X	
Smoking Cessation Counselling		X				X	X	
Register Visit in IRT/ RAMOS NG ^d		X	X	X	X	X	X	
Reversibility Testing ^e		X						
Spirometry			X ^f	X ^f	X ^f	X ^f		
Device training and registration		X	X					
Exacerbation Assessment		X	X	X	X	X	X	X
SGRQ-C ^g			X		X	X		
BDI ^g			X					
TDI ^g					X	X		
CAT ^g		X						
eDevice close out ^h			X			X	X	
Physical examination ⁱ		X				X	X	

Protocol Activity	Pre-Screen	Screen	Treatment				Follow Up	
	Visit 0 Pre-screen	Visit 1 Screening	Visit 2 Randomisation	Visit 3	Visit 4	Visit 5	Early Withdrawal Visit	Safety Follow-up Contact
Study Week		Week -2	Week 0	Week 4	Week 12	Week 24		1 week Fw-up
Window		-3/+8d		-4/+2d	-8/+6d	-8/+6d		-1/+4d
Adverse Events Assessment		X	X	X	X	X	X	X
Vital signs ^j		X		X		X	X	
ECG		X				X ^k	X ^k	
Chest X-ray ^l		X						
Pulse oximetry ^m			X					
Blood draw for PK					X ⁿ	X ^o		
Blood Draw for Genetics research						X ^p		
Haematology/biochemistry ^q		X				X	X	
Urine Pregnancy Test ^r		X		X	X	X	X	
Hepatitis B and C tests		X						
Dispense study treatment			X	X	X			
Administer study treatment in clinic ^s			X	X	X	X	X	
Assess study treatment compliance				X	X	X	X	
Collect study treatment				X	X	X	X	
Dispense albuterol/salbutamol		X	X	X	X			
Collect albuterol/salbutamol			X	X	X	X	X	
Issue/review paper diary ^t		X	X	X	X	X	X	

- Informed consent must be conducted at the Pre-screen Visit prior to performing any study procedures including the changing or withholding of medications. The (IC) may be given at Screening Visit 1 if the subject does not take or has not taken any protocol excluded medications.
- Genetics research consent may be obtained at the same time as the study IC and must be obtained prior to obtaining a genetic blood sample.
- Demography may be captured at either the Pre-screen Visit or Screening Visit (for subjects who do not have a Pre-screen Visit).
- The IRT will be used for randomisation, emergency unblinding and study treatment supply management (Please refer RAMOS NG IRT manual for more information)
- At Screening Visit 1 both pre and post-bronchodilator spirometry will be conducted. Pre-bronchodilator spirometry will be performed prior to the subject taking their morning dose of their usual COPD treatment, between 6am and 11am and after withholding rescue albuterol/salbutamol for ≥4 hours.
- At Visits 2-5 (and the Early Withdrawal Visit), pre-bronchodilator spirometry will be performed prior to taking the morning dose of study treatment, between 6am and 11am and after withholding rescue albuterol/salbutamol for ≥4 hours.

- g. Patient reported assessments should be conducted in the following order and before other study assessments: SGRQ-C, BDI/TDI.
- h. Close out eDevice for any subject who fails to randomize, withdraws early, or completes Visit 5.
- i. Physical examination may include height, weight, blood pressure, temperature, heart rate.
- j. Vital signs must be performed prior to spirometry and prior to taking morning dose of study medication.
- k. ECG to be obtained 15 - 45 minutes post-dose at treatment Visit 5 and Early Withdrawal Visit (if possible). If a subject is not dosed at Early Withdrawal, then an ECG can be taken at any time during the visit
- l. Chest X-ray (PA and lateral) is required at Screening (or historical x-ray obtained within 3 months prior to Screening) and at anytime there is a suspected pneumonia or a mod/severe exacerbation.
- m. Pulse oximetry must be performed at V2 and anytime there is a suspected pneumonia or a moderate or severe exacerbation.
- n. PK subset A: PK samples of 120 subjects at selected sites, to be obtained at two time points at Visit 4: pre-dose and in the window 5 to 15 minutes post-dose.
PK subset B: PK samples of 60 subjects at selected sites, to be obtained and Visit 4: pre-dose, 5-15min, 45-90min, 2.5-4h, 6-8h, 10-12h, 23-24h post-dose.
- o. PK subset A: PK samples of 120 subjects at selected sites, to be obtained at two time points at Visit 5: 5 to 15 minutes post-dose and 45 to 90 minutes post-dose.
- p. The genetics blood sample should be taken at V5 or at any visit after Randomisation (V2).
- q. Haematology and chemistry panels will include liver chemistry, and potassium and glucose levels.
- r. All female subjects of child bearing potential will have a urine pregnancy test at each visit except Visits 2 and follow-up.
- s. Subjects must withhold their morning dose of study treatment at each clinic visit and not take their study treatment dose until instructed to do so by study staff.
- t. Subjects will be issued a paper diary, at screening and other clinic visits (if required) in order to note any changes to concomitant medications and/or incidence of adverse events that may have occurred between clinic visits.

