7.3.3. Spirometry and Reversibility Testing

7.3.3.1. Spirometry

Spirometry measurements will be obtained using spirometry equipment that meets or exceeds the minimal performance recommendations of the ATS [Miller, 2005]. All sites will use standardised spirometry equipment provided by an external vendor. All subjects

will have spirometry performed at screening (pre- and post-salbutamol) and pre-dose at each scheduled clinic visit during the treatment period. For FEV₁ and FVC determinations, at least 3 acceptable spirometry efforts (with no more than 8) should be obtained. Acceptable spirometry efforts should have a satisfactory start of test and end of test (*e.g.* a plateau in the volume-time curve) and be free from artefacts due to cough, early termination, poor effort, obstructed mouthpiece, equipment malfunction, or other reasons [Miller, 2005].

The largest FEV₁ and FVC from the 3 acceptable efforts should be recorded, even if they do not come from the same effort. Spirometry must be performed as follows:

- Started approximately between 6:00AM and 11:00AM.
- After withholding albuterol/salbutamol for ≥ 4 hours.
- At Screening (V1), before the morning dose of their usual COPD medications.
- At Randomisation (V2) and all treatment visits, before the morning dose of study treatment.
- At Screening (V1), the CAT must be administered prior to spirometry
- At Randomisation (V2), V4 and V5, questionnaires must be completed prior to spirometry (SGRQ-C should be administered first followed by BDI/TDI)
- Subjects should refrain from smoking for 1 hour prior to each pulmonary function test.
- Subjects should abstain from drinking beverages with high levels of caffeine such as tea and coffee for 2 hours prior to each pulmonary function test.

A full description of the timing and conduct of spirometry procedures is provided in the SPM.

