5.1. Handling of Missing Data

The primary estimand for this study is a ‘de jure’ estimand. The primary analysis will use an ‘MPP’ population, using only data collected on-treatment and excluding data following protocol deviation or other event considered to impact the primary efficacy endpoint of change from baseline in trough FEV1 (as detailed in Section 10.1.2). This will evaluate the treatment difference if all subjects had taken the treatment as directed in the protocol which is considered the appropriate estimand for a determination of non-inferiority.

All data excluded from the primary efficacy analysis will be assumed to be missing at random. The sensitivity of the results to this assumption will be investigated by use of a ‘tipping point’ analysis as described in Section 7.1.2. This will evaluate various assumptions for the mean change from baseline in trough FEV1 for data excluded from the primary analysis, including scenarios where the response to treatment on FF/UMEC/VI is worse than that on FF/VI + UMEC and vice versa.

An alternative estimand will be evaluated. This will use the ITT population using all data collected on-treatment, for the change from baseline in trough FEV1. (No off-treatment

data for trough FEV1 were collected in this study.) All missing data will be assumed to be missing at random. This will evaluate the treatment difference in all randomized subjects, regardless of adherence to the protocol but assuming the treatment effect for subjects who discontinued treatment was similar to that for those who completed treatment.

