7.1.1.1. Spirometry data

Spirometry is assessed pre-treatment on Week 0, and pre-dose at Weeks 4, 12 and 24.

Spirometry data including FEV1 and FVC will be transferred from the vendor to GSK. When spirometry has been performed but the reading was unacceptable, a record in the database will indicate that the spirometry was performed but all data will be missing and will not be included in listings or summary displays.

The definition of baseline FEV1 and FVC is in Section [10.5.2.1](#) and of trough FEV1 and FVC is in Section [10.6.4](#).

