7.1.2. Planned Efficacy Statistical Analyses

Primary Statistical Analyses
Endpoint(s)

 ○ Trough FEV1
Model Specification

 ○ The primary endpoint of change from baseline in trough FEV1 will be analyzed in the mPP population, using a mixed model repeated measures (MMRM) analysis, including trough FEV1 recorded at each of Week 4, 12 and 24. The model will include covariates of baseline FEV1, stratum (number of long-acting bronchodilators per day during the run-in), Visit, geographical region, treatment and Visit by baseline interaction. A Visit by treatment interaction term will also be included to allow treatment effects to be estimated at each visit separately. ○ The variance-covariance matrix will be assumed unstructured. ○ Two models will be fitted; one with a response variable of trough FEV1, and one with a response variable of change from baseline in trough FEV1.
Handling of Missing Data for Analysis

 ○ No data were collected for subjects who prematurely discontinued study treatment. All missing and excluded data will be assumed to be Missing at Random (MAR). Sensitivity analyses to investigate the impact of this assumption will be conducted as described below.
Model Checking & Diagnostics

 ○ Refer to Appendix 11: Model Checking and Diagnostics for Statistical Analyses.
Model Results Presentation

 ○ Least Square (LS) mean and LS mean change from baseline with their corresponding standard errors (SEs) will be presented for each treatment by Visit, together with estimated treatment differences (FF/UMEC/VI vs. FF/VI+UMEC) and the corresponding 95% confidence intervals (CIs). ○ A plot of LS means change from baseline and 95% CIs from the model will be generated for each treatment by Visit.
Example SAS Code

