<pre>proc mixed data=<dataset>; class treatment visit cengroup stratum subjid; model endpoint=baseline stratum visit cengroup treatment visit*baseline visit*treatment / ddfm=kr; repeated visit/ subject=subjid type=un; lsmeans visit*treatment / cl diff e om=OMdset at (baseline)=(&blm.); ods output lsmeans=lsmeans; ods output diffs=diffs; run;</pre> 
where OMdset is a dataset with a row for every subject-visit combination that contains all of the covariates and blm is a macro variable containing the mean baseline for the subjects used in the analysis. This is used to derive the LS means using coefficients which are based on the subjects used in the analysis.

Sensitivity and Supportive Statistical Analyses

 ○ The above will be repeated for the ITT population. LS mean and LS mean change from

Sensitivity and Supportive Statistical Analyses

baseline with their corresponding SEs will be presented for each treatment by Visit, together with estimated treatment differences and the corresponding 95% CIs.

- A “tipping point” sensitivity analysis of trough FEV1 at Week 24 will be conducted for the mPP Population. This will explore the impact of missing data by using differing assumptions regarding the mean treatment effect in subjects who discontinue study treatment or have data excluded from the mPP Population analyses. Mean treatment effects investigated will range from a change from baseline of -150mL to +150mL in increments of 50mL. For each value of the assumed mean change from baseline on FF/UMEC/VI, the full range of values for the assumed mean change from baseline for FF/VI+UMEC will be investigated; thus including scenarios where subjects who discontinue FF/UMEC/VI have a lower treatment effect than those who discontinue FF/VI+UMEC and vice versa. The analysis results will be used to explore the conditions under which the conclusion of non-inferiority no longer holds.

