10.3. Appendix 3: Assessment Windows

In general, data will be reported according to the nominal time of clinic visits and assessments as specified in the protocol. For example, if a subject recorded values for the Week 4 visit that were actually made on the 21st day of treatment, they will be presented as Week 4 values in the summary tables.

Subjects that permanently stop study medication early between scheduled clinic visits should undergo all assessments listed for the Early Withdrawal Visit. Data collected at this visit will be listed and used in summary or analysis tables as part of the ‘worst case post baseline’ summary/analysis if appropriate.

Subjects that permanently stop study medication early at the time of a scheduled study visit will have data collected in the eCRF as part of the scheduled study visit.

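### Does the mismatch over spirometry at the Early Withdrawal Visit leave the trough FEV1 analysis unclear?

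*Protocol*

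**What the plan says.** Footnote f, attached to the Spirometry row in protocol 7.1 and copied into SAP 10.2, reads: "At Visits 2-5 (and the Early Withdrawal Visit), pre-bronchodilator spirometry will be performed prior to taking the morning dose of study treatment". In both tables that row is marked at Visits 2 to 5 and blank under Early Withdrawal.

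Protocol 7.3.3.1 says that subjects "will have spirometry performed at screening (pre- and post-salbutamol) and pre-dose at each scheduled clinic visit during the treatment period". SAP 7.1.1.1 says "Spirometry is assessed pre-treatment on Week 0, and pre-dose at Weeks 4, 12 and 24". Neither names the Early Withdrawal Visit. Protocol section 7 treats the table as binding: "Protocol waivers or exemptions are not allowed with the exception of immediate safety concerns".

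On conduct at withdrawal, SAP 10.3 says "Subjects that permanently stop study medication early between scheduled clinic visits should undergo all assessments listed for the Early Withdrawal Visit". It adds that data from that visit are listed and enter tables only within a worst-case post-baseline summary, where appropriate. Subjects who stop at a scheduled visit have their data recorded under that visit.

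On use, SAP 5.1 describes the alternative estimand: "This will use the ITT population using all data collected on-treatment, for the change from baseline in trough FEV1". It notes that no off-treatment trough FEV1 was collected. SAP 7.1.2 states more broadly: "No data were collected for subjects who prematurely discontinued study treatment".

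**The concern.** The footnote and the row give different answers on whether the primary variable is measured at withdrawal. The blank cell does not look accidental to a site reading the table: other rows, such as ECG and vital signs, carry a mark there. An instruction to do everything listed for the visit cannot settle what is listed, and with waivers barred a site has reason to worry about either reading.

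The SAP then seems to pull two ways. SAP 10.4.2 counts assessments up to one day after the treatment stop date as on-treatment, so a withdrawal FEV1 could fall within the ITT estimand's data. Yet trough FEV1 has no definition at that visit, and SAP 7.1.2 suggests that no such data exist.

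At stake would be the last FEV1 before a subject leaves the study. The missing-at-random assumption is tested by a grid of assumed means: "Mean treatment effects investigated will range from a change from baseline of -150mL to +150mL in increments of 50mL". A measured value near the time of stopping might show, by arm, which cells of that grid are believable.

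**Working it through.** **Is the value modelled under the current text?**

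1. SAP 10.6.4 defines the trough value only at Weeks 4, 12 and 24, as the pre-dose assessment.
2. SAP 7.1.2 fits the primary mixed model to those three visits and repeats the same analysis for the ITT population.
3. The on-treatment scope in SAP 5.1 refers to change from baseline in trough FEV1, which point 1 has already confined to scheduled visits.
4. SAP 10.3 sends stand-alone withdrawal data to listings and worst-case summaries. The worst-case, maximum and minimum definitions in SAP 10.6.3 cover ECG, vital signs and laboratory tests, not FEV1.
5. Listing 9 in SAP 10.13.9 covers raw FEV1 and FVC.

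Together these give one answer: a withdrawal-visit FEV1 is listed and not modelled. Week 4 and Week 12 values already recorded, and values from subjects who stop at a scheduled visit, stay available to the model, subject to the usual exclusions.

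**Do the row and footnote forbid each other?** No. A blank cell prohibits nothing, and the footnote is part of the table. A site that performs the test breaches no text. Protocol 7.3.3.1 concerns scheduled treatment-period visits, whereas the table places Early Withdrawal under follow-up.

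**Do SAP 5.1 and 7.1.2 disagree?** Only if the 7.1.2 sentence is read literally. It would then deny the Week 4 and 12 values that the same model uses for subjects who stop later. It must mean data after discontinuation, as SAP 5.1 says.

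**Size.** Inputs from protocol 9.2.1: SD 220 mL, margin 50 mL, true difference 0, one-sided 2.5%, 90% power, 816 evaluable, 20% lost, 1020 randomised.

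- Plan's own figure: n per arm = 2 × [220 × (1.960 + 1.282) / 50]² ≈ 407, or 814 in total against 816 stated. Power at 408 per arm is 90.1%. 816 / 0.80 = 1020. The figures reproduce, and this point alters none of them.
- Ceiling on subjects: 1020 - 816 = 204. This includes subjects excluded while still on treatment, who have no withdrawal visit. The documents give no split.
- Tipping difference, with 510 per arm, observed difference 0 and a fraction f imputed in each arm: SE = 220 × √(2/510) = 13.8 mL. Solving f × d - 1.96 × 13.8 = -50 gives d ≈ -115 mL at f = 0.20 and -230 mL at f = 0.10. On the 7 × 7 grid, 4 + 3 + 2 + 1 = 10 of 49 cells lie beyond the first value and 2 + 1 = 3 beyond the second.
- Precision of a by-arm withdrawal comparison: half-width = 1.96 × 220 × √(2/n). If 10% of the 204 are usable, n = 10.2 per arm and the half-width is 191 mL. If 50%, n = 51 and it is 85 mL.
- A half-width below 115 mL needs n > 2 × (431.2 / 115)² ≈ 28.1, so 29 per arm, or 58 of the 204 (28%).

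The 10% to 50% range is an assumption. The 220 mL is a model residual SD, borrowed here for a comparison it was not estimated for.

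**The case for a change.** The strongest case for acting is that repair is cheap and the visit is the last chance to measure FEV1. The timing could work: the table provides for dosing in clinic at withdrawal, with the morning dose withheld, so a pre-dose reading is possible. SAP 10.7.1 gives named rules for vital signs, laboratory tests and ECG at withdrawal but none for spirometry. A supportive model could place each withdrawal value at the next scheduled visit, and a by-arm summary could sit beside the tipping-point table.

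Part of this stands. The mismatch is in both documents, an FEV1-specific sentence is absent, and collection may vary between sites. The proposed analyses are harder to defend. Moving a value to the next visit can label a Week 13 measurement as Week 24, against the nominal-visit convention of SAP 10.3. Footnote k foresees subjects who are not dosed at withdrawal, so some readings may not be true on-treatment troughs. The by-arm summary becomes useful only if well over a quarter of the 204 supply a valid reading, and the 204 is itself a ceiling. The missing-at-random assumption is already probed by the 49-scenario grid. New collection instructions would also come late: SAP 10.8.1 already tabulates 398 + 252 + 215 + 194 = 1059 subjects against a target of 1020.

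**Conclusion.** No change to the plan is called for. The blank cell against footnote f is a clerical slip, and the sentence in SAP 7.1.2 is loose wording for what SAP 5.1 states correctly. The missing FEV1-specific rule is a gap that an analyst fills in only one way from SAP 10.3, 10.6.4 and 7.1.2: the value is listed, and the primary and ITT models use Weeks 4, 12 and 24. Settling the mismatch either way leaves every planned estimate, interval and non-inferiority conclusion as it is.

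What is forgone is a descriptive look at FEV1 near discontinuation, with a half-width of roughly 85 to 191 mL against a tipping difference of about -115 mL. Those figures assume a 10% to 50% usable fraction, SD 220 mL, an observed difference of 0 and 20% imputed in each arm. They gauge only what an added summary could show. The conclusion that the planned analyses are unaffected rests on the text alone.

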7.2. Screening and Critical Baseline Assessments

No study related procedures may be performed until the informed consent form has been signed by the subject. A pre-screening visit may be required in order to administer the informed consent before any changes are made to the subject's current medical regimen. Selection and modification of the subject's medications prior to study participation is based on the physician's judgment according to sound medical practice, principles, and each subject's needs. A subject's treatment must not be changed merely for the purpose of enabling the subject's participation in the study. The informed consent may be given at the Screening Visit (V1) if the subject does not take or has not taken any protocol excluded medications.

During the pre-screening visit (V0) each subject will have the following procedures performed. The following demographic parameters will be captured:

- Year of birth, sex, race and ethnicity.
- Concomitant medication review.

The additional following critical baseline assessments will be conducted at Screening (V1):

- Medical history including COPD history (comprised of COPD type [emphysema and/or chronic bronchitis]), smoking history, COPD exacerbations history, smoking status and previous and/or current medical conditions.
- Concomitant Medications review (COPD concomitant medications in the 3 months prior to Screening)
- COPD exacerbation assessment (documented history of exacerbation(s) in the 12 months prior to Screening)
- Cardiovascular medical history/risk factors
- Inclusion/Exclusion criteria assessment
- COPD Assessment Test (CAT)
- Physical examination
- Pulse rate, blood pressure measurements
- 12-lead ECG
- Pre- and post-albuterol/salbutamol spirometry (reversibility)
- SAE assessment (if related to study participation)
- Chest X-Ray [or historical radiograph obtained within 3 months prior to Screening (V1)]
- Laboratory assessments (chemistry and hematology, hepatitis and pregnancy testing)

In addition the following procedures must be completed at Screening (V1):

- Smoking cessation counseling
- Electronic device training
- Dispense albuterol/salbutamol

